6.5. Biomarkers

As yet, no clear surrogate endpoints have been widely accepted that clearly define clinical outcomes for the multi-organ system manifestations of SLE. However autoantibodies have been shown to be important early markers of specific disease processes or severity in SLE [Hahn, 1998; Leslie, 2001; Ravirajan, 2001] and are associated with disease activity [Villarreal, 1997]. Therefore autoantibody levels will be included as endpoints.

Collect blood samples as specified in the appropriate Time and Events schedule (Table 2 or Table 3), in order to assess the following endpoints:

• Percent change from baseline:

-Total serum immunoglobulin (IgG and other isotypes: IgM and IgA).

-Autoantibodies (anti-dsDNA) and complement (C3, C4).

 Percent change in absolute B cell subsets (CD20+, CD20+/27+ memory, CD20+/27naïve, CD20+/69+ activated, CD20+/138+ plasmacytoid, CD19+/27_{BRIGHT}/38_{BRIGHT} SLE subset and CD20-/138+ plasma cells).

All biomarker samples will be analysed centrally.

6.6. Pharmacokinetics

Collect blood samples for measurement of serum belimumab concentrations from subjects in the treatment holiday and control groups at selected sites at the times specified in the Time and Events Table (Table 2). Only one PK sampling for the treatment holiday group between Weeks 0 and 16 can be performed at any time during the visit. Otherwise, sampling must be performed prior to dosing (pre-dose sample) at Day 0 and Weeks 8 and 16. Sampling must be performed pre-dose and post-dose (at the end of the belimumab infusion) at Weeks 24 and 52 (or earlier if belimumab is re-started before Week 24 in the event of a severe flare by using the escape option). For non-dosing visits, assessment can be performed once at any time during the subject's visit. Subjects in the long-term discontinuation group will have one PK sampling performed at any time during the visit between Weeks 0 and 24. PK sampling for the long-term discontinuation group is not performed after Week 24. Long-term discontinuation subjects withdrawing before Week 24 will have one PK sampling performed at any time during the EXIT visit. PK sampling for long-term discontinuation subjects withdrawing after Week 24 is not performed at the EXIT visit. Samples will be analysed at a central laboratory. PK assessment will also be used to determine belimumab concentration in confirmed positive immunogenicity samples.

6.7. Pharmacogenetic Research

Collect a blood sample for pharmacogenetics (PGx) from consenting subjects except those recruited from Study BEL114333 (who have already provided a sample as part of that study). Samples for PGx must be drawn **prior** to dosing as appropriate.

Information regarding PGx research is included in Appendix 6.

7. DATA MANAGEMENT

For this study subject data will be entered into GSK defined electronic case report forms (eCRFs), transmitted electronically to GSK or designee and combined with data provided from other sources in a validated data system.

Management of clinical data will be performed in accordance with applicable GSK standards and data cleaning procedures to ensure the integrity of the data, e.g., removing errors and inconsistencies in the data. Adverse events and concomitant medications terms will be coded using MedDRA and an internal validated medication dictionary, GSKDrug. eCRFs (including queries and audit trails) will be retained by GSK, and copies will be sent to the investigator to maintain as the investigator copy. In all cases, subject initials will not be collected or transmitted to GSK according to GSK policy.

8. DATA ANALYSIS AND STATISTICAL CONSIDERATIONS

Originally a total of approximately 135 subjects (50 in the treatment holiday group, 50 in the control group, and 35 in the long term discontinuation group) were planned to be enrolled in this study. After 36 months had elapsed since study start, a reduction in sample size was agreed to with regulatory authorities, and a total of at least 71 patients (at least 10 in treatment holiday, at least 26 in the control group and 35 in the long term discontinuation group) will be the target sample size to be enrolled in this study. The total sample size is based on practical considerations on the availability of subjects from other ongoing belimumab studies, rather than on statistical considerations. Since this is a non-randomized study, results will be descriptive only, and not intended to be inferential. No power calculations were made in the determination of sample size for this study. However, the total of subjects is expected to provide adequate information to characterize time to SLE flare. Table 4 shows the flare rates for the pooled BLISS studies.

ISE Table	Analysis	Placebo	1 mg/kg	10 mg/kg
Т57	Percentage of Subjects with Flare Over 52 Weeks	81.5%	74.6%	74.6%
TAC411	Percentage of Subjects with Flare Over 52 Weeks Post Week 24	68.5%	54.7%	57.5%
TAC613	Percentage of Subjects with Flare Over 52 Weeks Among SRI Wk 52 Responders	73.4%	69.8%	67.4%

Table 4 Flare Rates from Pooled BLISS Studies

8.1. Data Analysis Considerations

8.1.1. Analysis Populations

The primary analysis population will be the Intent-to-treat (ITT) population. The ITT population will consist of all subjects enrolled in the study.

8.1.2. Primary Efficacy Analysis

Time to first SLE flare will be analyzed using a time-to-event analysis. Time to first SLE flare is defined as the number of days from Day 0 of the BEL116027 study to the first occurrence of a SLE flare. If a subject withdraws from the study or completes week 52 without a SLE flare, time to the first SLE flare will be censored at the time of the last observation (last visit measuring flare). However, if a subject receives prohibited medication during the study, the subject will be considered as having a SLE flare at the time the medication is started. Data observed at or prior to the Day 0 visit will not be included in this analysis.

8.1.3. Analysis of Additional Efficacy Endpoints

For the primary analysis of the additional efficacy and biomarkers, the baseline will be defined as study Day 0 of the original parent study. Additionally, for some of the endpoints, a secondary analysis will be performed by defining the baseline as Day 0 of the BEL116027 study.

The major analysis of the additional efficacy and biomarkers will include descriptive tabulation of secondary endpoints by treatment group according to the treatment group they are assigned to in the BEL116027 study.

8.1.4. Safety Analysis

AEs will be graded for severity by the investigator using Adverse Event Severity Grading Tables (Appendix 6) or the grades in Section 6.4.8, as appropriate. The frequency of AEs will be tabulated by MedDRA system organ class and preferred term and by treatment groups, according to the treatment group that the subjects were assigned to in the BEL116027 study. Additional analysis may be performed based on event rates adjusting for subject-years on study agent. The number of subjects with AEs and the incidence rate of AEs will be summarised in each 6-month time interval. AEs will also be summarised by MedDRA SOCs and preferred terms for those that are considered to be at least possibly related to study agent and those that are considered to be severe (Grade 3 and Grade 4). Discontinuations due to AEs will be summarised.

The frequency of laboratory abnormalities will be tabulated by treatment group. Laboratory values will be assessed for significant changes from baseline. Laboratory toxicity will be graded using Adverse Event Severity Grading Tables when possible. Shift tables will be used to determine if subjects move from normal to abnormal during the course of the study. Shifts of ≥ 2 grades and Grade 3 or Grade 4 laboratory abnormalities will be summarised.

Immunogenicity (anti-belimumab antibodies) will be summarized at baseline and during treatment and follow-up.

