2.1. Changes to the Protocol Defined Statistical Analysis Plan

Changes from the originally planned statistical analysis specified in the protocol are outlined in Table 2.

	otocol	Reporting & Analysis Plan		
Statistical Analysis Plan		Statistical Analysis Plan	Rationale for Changes	
•	Partial prothrombin time (PTT) is collected	 Activated partial prothrombin time (aPTT) time is analyzed 	aPTT was collected instead of PTT	
•	Section 8.1.3 states that for the primary analysis of the additional efficacy and biomarkers, the baseline will be defined as study Day 0 of the original parent study. Additionally, for some of the endpoints, a secondary analysis will be performed by defining the baseline as Day 0 of the BEL116027 study.	• The baseline for each endpoint is defined per Section 6.1 of the protocol.	The protocol was inconsistent in the definition of baseline. See RAP Section 5.3 for clarification	
•	Immunogenicity is listed as a secondary endpoint in Protocol Section 6.1.2., but as an exploratory laboratory parameter in the Time and Events table.	 Immunogenicity is defined as a secondary endpoint. 	 The protocol was inconsistent, so the correct category was used in the RAP. 	
•	Renal flares are not listed as an endpoint in Protocol Section 6.1.2 nor described in Protocol Section 8, but are defined in Protocol Section 6.1.4	 Renal flares are included as an exploratory endpoint in RAP Section 2.2. 	 The protocol was inconsistent, so the endpoint was correctly specified in the RAP. 	
•	The definition of renal flare contained a typographical error and referenced an increase rather than a decrease in GFR. This was corrected in a note to file.	 The RAP specifies the correct definition, referencing a decrease in GFR. 	The protocol was incorrect.	
•	Protocol Section 6.1.3 lists percent change in PGA.	 The RAP specifies change from baseline in PGA instead. 	Change from baseline is more clinically relevant and interpretable, particularly in the case of low baseline scores.	
•	Protocol Section 6.1.2 lists one time interval for percent change in B-cell subsets from Week 24, i.e., Week 24 to 52.	 In addition to this, the RAP specifies percent change from Week 24 to 32 and Week 24 to 40. 	The additional time intervals facilitate interpretation of the changes following the treatment holiday phase.	

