7. EFFICACY ANALYSES

For all efficacy analyses, results for the TH group will be presented for the treatment holiday (TH) and re-start (RS) phases separately.

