8.1. Adverse Events Analyses

Adverse events analyses including the analysis of adverse events (AEs), serious adverse events (SAEs), and other significant AEs will be based on GSK Core Data Standards. The details of the planned displays are provided in Appendix 11: List of Data Displays.

Adverse events will be coded to the current MedDRA dictionary version available at the time of reporting.

Only treatment emergent AEs will be summarized (see Section 13.4.1). Any AEs that were ongoing in the upon entry into this will be listed and flagged with a footnote

An overall summary of AEs will be presented showing the number (%) of subjects with at least one of the following: AE, related AE, SAE, severe AE, SAE and/or severe AE, AE resulting in study treatment discontinuation, and deaths.

The number of events and the number (%) of subjects experiencing an AE by SOC, SOC and PT, and PT will be summarized for each of the AE categories below.

- All
- Serious
- Severe
- Study agent Related
- Resulting in discontinuation of study treatment

The data will be sorted by overall decreasing frequency of the SOC, by overall decreasing frequency of the SOC and then decreasing frequency of PT within the SOC, and by overall decreasing frequency of the PT, as applicable. Only SOCs with observed AE PTs will be presented. If the frequency for any two or more adverse events is equal, the events will be presented in alphabetical order by SOC/PT as applicable.

Summaries of AEs frequency by SOC and severity will also be provided. For these displays, the number and percentage of subjects will be summarized as mild, moderate, or severe based on the maximum severity observed across all PTs within the SOC for a given subject.

The hierarchical relationship between MedDRA SOCs, PTs, and verbatim text will be displayed in a table for all AEs.

A listing of which subjects reported each AE will be produced. AEs will be grouped and sorted by SOC and PT. A listing of Infusion Related Systemic Reactions will be produced.

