13.4. Appendix 4: Study Phases and Treatment Emergent Adverse Events

13.4.1. Treatment Phases

- Visits, assessments and events will be classified according to the time of occurrence relative to the following cut-point dates for each treatment group.
- For convenience and ease of data presentation, the 52-Week Treatment Phase has the same name designation for all three treatment groups, even though the LTC group does not receive treatment at all during this phase and the TH group receives treatment for only the second half of the phase.
- Only the TC and TH groups are eligible to participate in the Maintenance Phase.
- If an AE start date falls on the Day 0 date, then it will be considered treatment emergent (i.e., fall in the 52-week treatment phase). If a concomitant medication start date falls on the Day 0 visit date, the concomitant medication will be considered to fall in the 52-week treatment phase. Any other assessments that fall on the Day 0 visit date will be considered to occur in the pre-study phase.
- For the TC group, if the first infusion date differs from the Day 0 visit date, then the first infusion date will be used as the phase cut-point.
- Other than Day 0, if an assessment or event occurs on the same date as a phase cutpoint, then the event will be considered to fall in the previous phase. For example, if a new prednisone dose starts on the same date as the Week 24 visit date and then continues for a total of 7 days, then the first day of that prednisone dose will fall into the Holiday Phase and the remaining 6 will fall into the Re-start phase.
- For AEs, if the AE Onset date is missing, then the AE will be considered to occur in the 52-week treatment phase.
- For the TH group, a subject who re-starts treatment prior to Week 24 will not have a Re-Start phase.

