13.11.7. Safety Tables

Safety:	Safety: Tables					
No.	Population	Title	Programming Notes	Priority Headline Results Denoted by H		
Concor	mitant Medicati	ons				
3.1.	ITT	Concomitant Medications by ATC Level 1 and ATC Level 4 Term for the 52-Week Treatment Phase	ICH E3			
Study A	Agent Exposure	9				
3.2.	ITT	Study Agent Exposure (52-Week Treatment Phase)	ICH E3			
SLICC						
3.3.	ITT	SLICC/ACR Damage Index Change from Baseline (52- Week Treatment Phase)	Other/exploratory endpoint			
Advers	e Events		·			
3.4.	ITT	Adverse Events (52-Week Treatment Phase)	Benlysta standard	Н		
3.5.	ITT	Adverse Events by SOC (52-Week Treatment Phase)	Benlysta standard			
3.6.	ITT	Serious Adverse Events by SOC (52-Week Treatment Phase)	Benlysta standard			
3.7.	ITT	Study Agent Related Adverse Events by SOC (52-Week Treatment Phase)	Benlysta standard			
3.8.	ITT	Adverse Events Resulting in Study Agent Discontinuation by SOC (52-Week Treatment Phase)	Benlysta standard			

Safety:	Safety: Tables				
No.	Population	Title	Programming Notes	Priority Headline Results Denoted by H	
3.9.	ITT	Adverse Events by SOC and PT (52-Week Treatment Phase)	ICH E3	Н	
3.10.	ITT	Serious Adverse Events by SOC and PT (52-Week Treatment Phase)	Benlysta Standard	Н	
3.11.	ITT	Study Agent Related Adverse Events by SOC and PT (52-Week Treatment Phase)	ICH E3		
3.12.	ITT	Adverse Events Resulting in Study Agent Discontinuation by SOC and PT (52-Week Treatment Phase)	IDSL	Н	
3.13.	ITT	Adverse Events by PT (52-Week Treatment Phase)	Benlysta Standard		
3.14.	ITT	Serious Adverse Events by PT (52-Week Treatment Phase)	Benlysta Standard		
3.15.	ITT	Study Agent Related Adverse Events by PT (52-Week Treatment Phase)	Benlysta Standard		
3.16.	ITT	Adverse Events Resulting in Study Agent Discontinuation by PT (52-Week Treatment Phase)	Benlysta Standard		
3.17.	ІТТ	Common (>5%) Non-Serious Adverse Events by SOC and PT (52-Week Treatment Phase) (Number of Subjects and Occurrences)	FDAAA, EudraCT		
3.18.	ІТТ	Serious Adverse Events by SOC and PT (52-Week Treatment Phase) (Number of Participants and Occurrences)	FDAAA, EudraCT	Н	
3.19.	ITT	Adverse Events by SOC and PT and Maximum Severity (52- Week Treatment Phase)	IDSL		

Safety:	afety: Tables					
No.	Population	Title	Programming Notes	Priority Headline Results Denoted by H		
3.20.	ITT	Relationship Between System Organ Class and Verbatim Text (52-Week Treatment Phase)	IDSL			

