3.21.	ITT	Adverse Events of Special Interest by Category (52-Week Treatment Phase)	Benlysta Standard	н		
3.22.	ITT	Adverse Events of Special Interest by Category and Infusion for Treatment Holiday Group Re-Start Phase	Benlysta Standard			
Labora	tory Parameter	'S				
3.23.	ITT	Laboratory Results by Visit: Hematology (52-Week Treatment Phase				
3.24.	ITT	Laboratory Results by Visit: Liver Function (52-Week Treatment Phase)				
3.25.	ITT	Laboratory Results by Visit: Electrolytes (52-Week Treatment Phase)				
3.26.	ITT	Laboratory Results by Visit: Other Chemistries (52-Week Treatment Phase)				
3.27.	ITT	Laboratory Results by Visit: Urinalysis (52-Week Treatment Phase)				
3.28.	ITT	Laboratory Results by Visit: Immunoglobulins (52-Week Treatment Phase)				
3.29.	ITT	Worst Laboratory Toxicity Grade: Hematology (52-Week Treatment Phase)	ICH E3			

Safety:	Tables			
No.	Population	Title	Programming Notes	Priority Headline Results Denoted by H
3.30.	ITT	Worst Laboratory Toxicity Grade: Liver Function (52-Week Treatment Phase)	ICH E3	
3.31.	ITT	Worst Laboratory Toxicity Grade: Electrolytes (52-Week Treatment Phase)	ICH E3	
3.32.	ITT	Worst Laboratory Toxicity Grade: Other Chemistries (52-Week Treatment Phase)	ICH E3	
3.33.	ITT	Worst Laboratory Toxicity Grade: Urinalysis (52-Week Treatment Phase)	ICH E3	
3.34.	ITT	Worst Laboratory Toxicity Grade: Immunoglobulins (52-Week Treatment Phase)	ICH E3	
3.35.	ITT	Laboratory Toxicity Grade Worsening of at Least 2 Grades from Baseline: Hematology (52-Week Treatment Phase)	Benlysta Standard	
3.36.	ITT	Laboratory Toxicity Grade Worsening of at Least 2 Grades from Baseline: Liver Function (52-Week Treatment Phase)	Benlysta Standard	
3.37.	ITT	Laboratory Toxicity Grade Worsening of at Least 2 Grades from Baseline: Electrolytes (52-Week Treatment Phase)	Benlysta Standard	
3.38.	ITT	Laboratory Toxicity Grade Worsening of at Least 2 Grades from Baseline: Other Chemistries (52-Week Treatment Phase)	Benlysta Standard	
3.39.	ITT	Laboratory Toxicity Grade Worsening of at Least 2 Grades from Baseline: Urinalysis (52-Week Treatment Phase)	Benlysta Standard	
3.40.	ITT	Laboratory Toxicity Grade Worsening of at Least 2 Grades from Baseline: Immunoglobulins (52-Week Treatment Phase)	Benlysta Standard	
3.41.	ITT	Laboratory Reference Range Shifts from Baseline by Visit: Hematology (52-Week Treatment Phase)	Benlysta Standard	

Safety: Tables				
No.	Population	Title	Programming Notes	Priority Headline Results Denoted by H

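### The SAP drops the protocol's adverse event summary by 6-month interval without logging it, plans no AE rate, and never says how the holiday group's off-drug and on-drug AEs will be shown

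*Protocol*

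**What the plan says.** Protocol Section 8.1.4 states the interval summary as a commitment: "The number of subjects with AEs and the incidence rate of AEs will be summarised in each 6-month time interval". The sentence before it, on event rates adjusted for subject-years on study agent, is only permissive.

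SAP Section 8.1 replaces this with counts and percentages: "The number of events and the number (%) of subjects experiencing an AE by SOC, SOC and PT, and PT will be summarized". It names no time interval and no rate. In Appendix 11, Tables 3.4 to 3.21 all carry the label 52-Week Treatment Phase. The one AE table whose title names a TH phase is Table 3.22, "Adverse Events of Special Interest by Category and Infusion for Treatment Holiday Group Re-Start Phase", which covers only the on-drug period.

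SAP Section 2.1 says "Changes from the originally planned statistical analysis specified in the protocol are outlined in Table 2". That table has no entry for the AE summary, although it logs changes as small as aPTT replacing PTT.

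On phases, SAP Section 13.4.1 says "Visits, assessments and events will be classified according to the time of occurrence relative to the following cut-point dates for each treatment group". The TH diagram in 13.4.1.1 then divides the row containing adverse events into Holiday and Re-start phases. The corresponding rows for TC (13.4.1.2) and LTD (13.4.1.3) are undivided. The instruction to display the two TH phases apart is in Section 7: "For all efficacy analyses, results for the TH group will be presented for the treatment holiday (TH) and re-start (RS) phases separately". Section 8 has no equivalent sentence for AEs.

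**The concern.** The study exists to describe what happens when belimumab is withdrawn for 24 weeks and then reintroduced for 28, and safety is a stated secondary objective. For AEs in the TH group, the natural description is off drug against on drug, next to the same calendar periods in TC and LTD. The protocol's interval summary would have come close to this for all groups. Once it is gone, no AE table title isolates the off-drug period, and no planned measure corrects for different lengths of follow-up. A reader of the SAP also cannot tell that a protocol-specified safety summary has been removed.

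**Working it through.** The documents give no AE rate, so there is no planned figure to reproduce. The rates and rate ratios below are assumptions, shown over a range.

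**Inputs from the documents**
- TH: 24 weeks off drug and 28 weeks on drug (Protocol Section 2.1).
- Enrolled: TH 12, TC 29, LTD 39 (SAP Section 2.3).
- AE measures: events and number (%) of subjects (SAP Section 8.1).

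**Case A: TH tables pool the 52 weeks.** Assume constant rates, full follow-up and restart at Week 24. With off-drug to on-drug rate ratio RR, the pooled rate relative to the on-drug rate is (24 × RR + 28)/52.
- RR = 1.5: (36 + 28)/52 = 1.23
- RR = 2: (48 + 28)/52 = 1.46
- RR = 3: (72 + 28)/52 = 1.92

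The share of the excess kept is 24/52 = 46% at any RR. On the SAP's own measure, subjects with at least one AE, take RR = 2 and on-drug rates of 0.2, 0.5, 1 and 3 per subject-year. The TH/TC ratio is 1.91, 1.79, 1.63 and 1.25 over the first 24 weeks, and 1.40, 1.32, 1.22 and 1.04 over 52 weeks.

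**Case B: TH is split, TC and LTD are not.** With the same true rate λ in every group, the expected proportion with at least one event over w weeks is 1 − exp(−λ × w/52). At λ = 0.5:
- TH Holiday, 24 weeks: 1 − exp(−0.231) = 20.6%
- TH Re-start, 28 weeks: 1 − exp(−0.269) = 23.6%
- TC and LTD, 52 weeks: 1 − exp(−0.5) = 39.3%

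Over the range of λ, 24 weeks against 52 weeks gives 8.8% v 18.1% (0.2), 37.0% v 63.2% (1) and 75.0% v 95.0% (3). The gap comes only from time at risk.

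**What each remedy recovers.** Taking six months as 26 weeks (an assumption), the protocol's first interval holds 24 off-drug and 2 on-drug weeks. The apparent ratio is (24 × RR + 2)/26 = 1.46, 1.92 and 2.85 for RR = 1.5, 2 and 3, so 24/26 = 92% of the excess is kept. A cut at the Week 24/restart visit keeps all of it.

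**Precision.** With full follow-up, TH has 12 × 24/52 = 5.5 subject-years off drug and 12 × 28/52 = 6.5 on drug.

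**Boundary rule.** Section 13.4.1 places an event on a cut-point date, other than Day 0, in the previous phase. An AE on the day of the first restart infusion would therefore be a Holiday phase event. Yet Section 8.2.1.2 counts systemic reactions on the day of an infusion against the infusions of the Re-start phase.

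**The case against.** A reader might infer that the SAP pools the holiday group's off-drug and on-drug AEs, so that an off-drug excess is diluted. The documents do not establish this. Section 13.4.1.1 does divide TH adverse events by phase. The 52-Week Treatment Phase label proves nothing, because efficacy Tables 2.6 and 2.7 carry it too and Section 7 requires those to be split. The SAP calls the shared name a convenience, and the mock shells that would show the columns are not included. The dilution figures therefore hold only under one possible layout.

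Other points on the same side are fair. The Week 24/restart cut isolates the off-drug period better than a 6-month interval. Expected lupus signs and symptoms are not AEs unless more severe than expected (Protocol Section 6.4.2.1), so off-drug worsening will show mainly in flares and rebound. Table 3.22 covers re-exposure reactions, Listing 13 gives every AE, and Appendix 4 derives onset times, so timing can be recovered subject by subject. The study is descriptive and TH is small.

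These points lower the stakes but leave the omission in place. A rule for classifying events is not an instruction to display them, and a listing is not the summary the protocol promised. A split layout resolves the dilution but leaves the unequal follow-up uncorrected.

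**Conclusion.** The point holds in a limited form. It is established that the interval summary is gone, that no AE rate is planned, and that the SAP's table of changes is silent about both. How TH adverse events will be displayed is unresolved. The two consequences are alternatives: pooling would leave 46% of an off-drug excess rate, while splitting would compare 24- and 28-week percentages with 52-week ones (20.6% and 23.6% against 39.3% at 0.5 events per subject-year). Both rest on constant rates, full follow-up and assumed values that the documents do not supply. This is a reporting gap in a descriptive study. It deserves correction because it affects the main safety description and is easy to close.

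**What to change.** - In SAP Section 8 and Appendix 11, add AE tables with TH shown by Holiday and Re-start phase, and TC and LTD shown for Weeks 0-24 and Weeks 24-52. Give subjects, events, subject-years and rate in each cell.
- Use subject-years of follow-up in the period as the denominator. Time on study agent would be zero for LTD and for the Holiday phase.
- Extend the tables to SAEs and AESIs. This goes beyond the protocol, which commits only to AEs by 6-month interval.
- State how an AE on the day of the first restart infusion is assigned, and make that consistent with Section 8.2.1.2 and Table 3.22.
- Log any remaining departure from the 6-month wording in SAP Table 2, with a reason.

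The cost is a few extra descriptive tables from data already collected. Section 13.6.3 already derives follow-up time by TH phase for flare rates, so only a Week 24 split for TC and LTD is new. The estimates will be imprecise, particularly in TH, and should be presented as such.
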